#### Background

Acute pancreatitis (AP) is an inflammatory disease of the pancreas, most commonly caused by gallstones or excessive alcohol use. It represents a management challenge and a significant healthcare burden. The incidence of AP ranges globally from 5 to 30 cases per 100.000 inhabitants/year, and there is evidence that the incidence has been rising in recent years. The overall case-fatality rate for AP is roughly 5%, and it is expectedly higher for more severe stages of the disease [1, 2]. In most cases (80%), the outcome of AP is rapidly favorable [3]. However, acute necrotizing pancreatitis (ANP) may develop in up to 20% of cases and is associated with significant rates of early organ failure (38%), needing some surgical/endoscopic intervention (38%), and death (15%) [4].

In the United States, AP is a leading cause of inpatient care among gastrointestinal conditions: more than 270.000 patients are hospitalized for AP annually, at an aggregate cost of over 2.5 billion dollars per year [5]. In Europe, the UK incidence of AP is estimated as 15-42 cases per 100.000/year and is rising by 2.7% each year [6].

Several scientific societies published their clinical practice guidelines making recommendations on the management of AP [7] (Table\_1-4). These guidelines' main topics are the diagnosis, antibiotic treatment, management in the intensive care unit, surgical and operative management, and open abdomen management.

Audits about biliary AP have been performed in Italy, Germany, France, and England, with quite disappointing results [8-11]. Indeed, in these audits, the treatment of biliary AP differed substantially from the recommendations. For example, less than 15% of the responders stated that they strictly followed all recommendations included in the guidelines in Germany, and 25.8% of patients did not receive definitive treatment for biliary AP within one year in the UK [12].

A recent study from Singapore aiming to review the clinical management of patients with AP in an HPB referral center in the light of assessing the compliance to the 2013 International Association of Pancreatology (IAP)/American Pancreatic Association (APA) and the 2015 Japanese guidelines found that only 50% of patients received Ringer lactate for initial fluid resuscitation, 38.7% received antibiotics as prophylaxis, 21.4% of patients with severe AP had early enteral nutrition, and only 21.4% patients with biliary AP had index admission cholecystectomy despite the recommendations [13]. In

another recent study by a Canadian group, only 25% of patients with gallstones AP underwent a cholecystectomy on the same admission. Furthermore, only one-quarter of patients in whom an index admission cholecystectomy was not possible underwent ERCP with sphincterotomy, and only one-third of patients with gallstones AP and an imaging-confirmed obstructed common bile duct had an ERCP and sphincterotomy [14]. Slow implementation of the recommendation on early cholecystectomy has also been reported in a Danish survey seeking compliance with the recommendations of the national reference program for the treatment of patients with gallstone disease [15], and a similar lack of compliance with guidelines was found in Italy, mainly regarding indications for endoscopic and surgical management [16].

Conversely, a recent study from Sweden has shown that the recurrence rate and associated costs can be reduced by improved compliance to current AP guidelines. The authors found that 80% of patients with biliary AP underwent definitive treatment during their first attack (68% cholecystectomy, 17% ERCP and sphincterotomy, 15% both interventions) [17].

Moreover, significant overall differences between the practice of HPB specialists and non-specialists in gallstone AP have been reported, especially regarding severity assessment, indication and timing of requesting CT scan, nutritional support, and in common bile duct assessment before cholecystectomy [18].

These findings support the view that publication alone of nationally or internationally developed and approved guidelines is insufficient to modify the practice of non-specialists and raises the question of how best to spread guideline recommendations. Previous reports, including the one from France in 2012, have shown that major changes in biliary AP patients management were noticed since the French guidelines publication. In particular, after the publication of the mentioned guidelines, lipase levels were measured for establishing AP diagnosis by 99% (vs. 83% pre-guidelines), and a CT scan was performed at 48h by 69% (vs. 29% pre-guidelines) to evaluate AP severity. Antibiotic prophylaxis and enteral nutrition were proposed by 20% (vs. 57% pre-guidelines) and 58% (vs. 25% pre-guidelines) for necrotizing AP [19].

#### **Management of pancreatic necrosis**

Infection of pancreatic necrosis is the predominant driver of sustained morbidity and late mortality in patients with severe AP. The subset of patients with ANP may face a complicated and prolonged

clinical course, with an associated mortality of up to 30% if an infection develops in the necrotic collection [20, 21]. Optimal management of patients with pancreatic necrosis requires a multidisciplinary approach, and specific guidelines for this specific subgroup of patients have been recently released (Table\_5). Although antibiotic prophylaxis may prevent or reduce necrosis colonization, the results of RCTs evaluating this approach and meta-analyses do not support prophylaxis [22]. Consequently, internationally applicable recommendations are that intravenous antibiotic prophylaxis is not recommended to prevent infectious complications in AP. However, several global overviews assessing reports from across the world of the use of antibiotics in prophylaxis in AP have shown a spread diffusion of such behavior [23].

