#### **Primary outcomes**

- ! 30-day mortality: assessed by the number of AP patients with biliary etiology deceased during the non-pandemic period (2019) and the Covid-19 pandemic period (2020)
- ! 30-day morbidity: assessed by the number of AP patients with biliary etiology who experienced any type of AP-related complication within 30-days from the hospital admission during the non-pandemic period (2019) and the Covid-19 pandemic period (2020)

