#### **Study periods**

The pre-pandemic period runs from 01/01/2019 to 31/12/2019. The Covid-19 pandemic period runs from 01/01/2020 to 31/12/2020. Data will be entered in the database from 01/03/2021 to 31/08/2021.

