## Section 13 – 30-day Overall mortality (Yes/No)

## Section 14 – Post-cholecystectomy 30-day morbidity and mortality

- ! Post-cholecystectomy morbidity (Yes/No)
- ! Post-cholecystectomy mortality (Yes/No)
- ! 30-day hospital readmission (No/Yes-due to surgical complications/Yes-due to recurrent pancreatitis while awaiting interval cholecystectomy)

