	
 
accompanying an aggravated general condition. (1C)
 
! Infected pancreatic necrosis should be suspected when clinical symptoms and blood test findings deteriorate. Routine use of FNA is not required for diagnosis, and clinical signs and CT should be used for a comprehensive determination. If an aggravated general condition is observed, percutaneous drainage or endoscopic drainage should be given for diagnosis and treatment. (1C)
 
! If possible, therapeutic intervention for infected pancreatic necrosis should be performed after 4 weeks of onset, when the necrosis has been sufficiently walled off, or in other words, during WON period. (2C)
 
! During therapeutic intervention for infected pancreatic necrosis, percutaneous (retroperitoneal) drainage or endoscopic transluminal drainage should be first given, and if no improvement is achieved, necrosectomy should then be performed. Necrosectomy by endoscopic or retroperitoneal approach is recommended. (2B)
 

16. Post-ERCP pancreatitis	
 
Prophylactic temporary pancreatic stent placement is useful as an effective endoscopic procedure for the prevention of post-ERCP pancreatitis. This should only be performed in the high-risk groups for post-ERCP pancreatitis given the risks and cost. (2A)
 
The guidewire method is very likely to reduce the incidence of post-ERCP pancreatitis. (2A)
 
For the prevention of post-ERCP pancreatitis, the intrarectal administration of NSAIDs should be carried out for all cases undergoing ERCP with no contraindications. (2A)
 
(Other drugs should not be used as routine preventive measures, since their efficacy has been refuted or is uncertain.)
 

17. Clinical indicators (pancreatic bundles)	! A high rate of implementation of the pancreatitis bundles may contribute to improving prognosis of patients with severe acute pancreatitis. (1C)

From: Yokoe M, Takada T, Mayumi T, Yoshida M, Isaji S, Wada K, Itoi T, Sata N, Gabata T, Igarashi H, Kataoka K, Hirota M, Kadoya M, Kitamura N, Kimura Y, Kiriyama S, Shirai K, Hattori T, Takeda K, Takeyama Y, Hirota M, Sekimoto M, Shikata S, Arata S, Hirata K. Japanese guidelines for the management of acute pancreatitis: Japanese Guidelines 2015. J Hepatobiliary Pancreat Sci. 2015 Jun;22(6):405-32. doi: 10.1002/jhbp.259. Epub 2015 May 13. PMID: 25973947.

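### Mortality by timing of surgical necrosectomy cannot be read fairly from an undated 30-day death field, because operations after 4 weeks leave almost no counted time

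*Combined protocol and SAP*

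**What the plan says.** The primary objective is to find which guideline items, when disregarded, go with bad outcomes. Under Secondary outcomes, timing of surgical necrosectomy is one of the practices by which compliance is judged.

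Three of the tabled guidelines favour waiting about 4 weeks. Table 1, item 20, links postponement of surgery beyond 4 weeks from onset with lower mortality. Table 5, advice 6, prefers debridement delayed for 4 weeks. The table of the 2015 Japanese guidelines, item 15, says that, where possible, "therapeutic intervention for infected pancreatic necrosis should be performed after 4 weeks of onset".

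The outcomes are short. Morbidity counts patients with "any type of AP-related complication within 30-days from the hospital admission". Mortality is worded as "30-day mortality: assessed by the number of AP patients with biliary etiology deceased during the non-pandemic period (2019" and likewise for 2020, with no day from which the 30 days run. CRF Section 13 holds one item, "30-day Overall mortality (Yes/No", with no day of death. CRF Section 10, headed as 30-day morbidity, records necrosectomy timing in three bands from symptom onset: under 2, 2 to 4 and over 4 weeks. Statistical analysis plans logistic regression, with no landmark or time-dependent method.

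Management of pancreatic necrosis calls the related mortality late ("Infection of pancreatic necrosis is the predominant driver of sustained morbidity and late mortality in patients with severe AP") and describes necrotic collections "with an associated mortality of up to 30% if an infection develops in the necrotic collection".

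**The concern.** The guideline-concordant band for necrosectomy opens at about the time the counting of deaths closes. A patient operated on early is watched for weeks afterwards. One operated on just after week 4 is watched for days, and one operated on beyond day 30 from admission was necessarily alive on day 30 and can only be coded as a survivor.

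This is separate from the fact that a patient must survive to be operated on late. The unequal window would remain even if every patient survived to the operation.

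The objective is item by item, so a false association on one item is a false primary result. It would appear to confirm the guideline whether or not delay helps, and the rationale says the findings are meant to feed care bundles. Regression adjustment cannot repair it, because the uncounted deaths are not in the data.

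**Working it through.** The plan gives no figure of its own on this point, so there is nothing to reproduce first.

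**Inputs from the documents.** The 30-day horizon (Primary outcomes; CRF Section 13); the three timing bands from onset (CRF Section 10); the data-entry dates (Study periods).

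**Assumptions.** The mortality clock starts at admission. The lag from onset to admission is 0 to 7 days. The early operation is on day 10, 14 or 21 from onset. The late one is on day 29, the first day past 4 weeks and so the case kindest to the plan. Post-operative death risk R over 30 days is the same in both groups, 10% to 30%, at constant hazard. The Background gives 15% mortality in necrotizing disease and the necrosis section gives up to 30% once infected. Neither is a post-operative risk; they only place the range.

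**Step 1: counted days after the operation** = 30 + lag − operation day from onset, and never below 0.

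| Operation day | Lag 0 | Lag 1 | Lag 3 | Lag 7 |
|---|---|---|---|---|
| 10 | 20 | 21 | 23 | 27 |
| 14 | 16 | 17 | 19 | 23 |
| 21 | 9 | 10 | 12 | 16 |
| 29 | 1 | 2 | 4 | 8 |
| 35 | 0 | 0 | 0 | 2 |

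Between day 14 and day 29 the late patient has 29 − 14 = 15 fewer counted days at every lag shown.

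**Step 2: recorded mortality.** h = −ln(1 − R)/30; recorded risk = 1 − exp(−h × counted days). Example with R = 15%, lag 1, day 14 against day 29:
- h = −ln(0.85)/30 = 0.00542 per day
- early: 1 − exp(−17h) = 8.8%
- late: 1 − exp(−2h) = 1.08%
- odds ratio = (0.0108/0.9892)/(0.0880/0.9120) = 0.11, where the truth is 1

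**Step 3: range of the odds ratio** at R = 15%, late operation on day 29:

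| Early operation day | Lag 0 | Lag 1 | Lag 3 | Lag 7 |
|---|---|---|---|---|
| 10 | 0.05 | 0.09 | 0.17 | 0.28 |
| 14 | 0.06 | 0.11 | 0.20 | 0.33 |
| 21 | 0.11 | 0.20 | 0.33 | 0.49 |

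Changing R to 10% or 30% hardly matters: over all combinations the extremes are 0.045 (R = 30%, day 10, lag 0) and 0.493 (R = 10%, day 21, lag 7). Lag and operation day drive the result, not the death risk.

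**Step 4: would a real harm from delay show?** Take the Step 2 example and double the late hazard. Late recorded risk = 1 − exp(−2 × 0.00542 × 2) = 2.14%, and the odds ratio = (0.0214/0.9786)/(0.0880/0.9120) = 0.23. Delay would still look protective.

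**Step 5: is longer follow-up available?** 31/12/2020 + 90 days = 31/03/2021, which is 153 days before entry closes on 31/08/2021.

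**The case against.** **The horizon is conventional and the reach is small.** The Background puts necrotizing disease at up to 20% of cases and intervention at 38% of those: 0.20 × 0.38 = 7.6%, or about 30 of the minimum 400 patients, if those general rates apply. Late necrosectomy is a subset. This stands as a limit on how many patients are touched. It does not rescue the result for an item that the objective examines in its own right.

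**The size is not derivable.** The documents give no lag, no operation days, no hazard shape and no mortality clock, and late is never put in days. This stands, so a single odds ratio such as 0.11 should not be quoted as the bias.

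**A reader might extend the point further. The documents do not support that:**
- *Re-laparotomy.* Table 1, item 25, sets open-abdomen re-exploration within 24 to 48 hours, and the CRF bands differ by hours to days. A contrast of week 2 with week 4 does not arise.
- *Drainage.* Endoscopic drainage is a yes/no field without timing, so no early-against-late contrast is planned. Tables 1 and 5 also describe drainage without a 4-week wait.
- *Morbidity in general.* The outcome is any complication. A patient who reaches necrosectomy will usually already be a case, for example through infected necrosis.
- *The 2019–2020 comparison.* Both years share one window, so bias needs late harm to differ by year. The COVID-19 section does not mention necrosis intervention or late deaths.

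**Conclusion.** The point holds for one analysis: mortality by timing of surgical necrosectomy. With a 30-day clock from admission, the over-4-weeks band has almost no counted post-operative time. The planned logistic models would favour delay with no true difference, with an odds ratio of about 0.05 to 0.49 under the stated assumptions. The direction of this error follows from the window itself; the size is illustrative.

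The verdict depends on the admission clock, which the mortality outcome does not state. A clock from onset would match the lag 0 column. The point concerns only how deaths are counted and says nothing on when necrosectomy should be done. A reader might infer that both primary outcomes, or the pandemic comparison, are invalid at 30 days; that does not follow.

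**What to change.** 1. State in Primary outcomes that the 30-day mortality clock starts at admission.
2. Add to CRF Section 13: death during the index stay or by day 90 (yes/no, with day of death).
3. Record the day of necrosectomy, including operations after day 30, so that these are not entered as no necrosectomy because of the section's 30-day heading. Counting days from admission respects the rule against identifiable data.
4. Analyse the necrosectomy-timing item on death over equal time from the operation, for example 30 days after it, or on index-stay or 90-day death. The first equalises the window; follow-up to day 90 covers it in full for operations up to day 60 from admission (90 − 30).
5. Keep the 30-day outcomes for all other items. Extending every Section 10 complication field to day 90 is not needed.

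The cost is a few more chart fields and no change in care. Patients admitted after 01/12/2020 reach day 90 after entry opens on 01/03/2021, so their records should be completed later in the entry window. Some deaths after discharge or transfer will be missed; report index-stay death alongside as the more complete version. The fix does not remove selection by survival to the operation or confounding by severity, and the report should say so.

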#### **COVID-19 and management of AP**

In 2020, the spread of the virus Covid-19 had represented a pandemic, which also profoundly impacted the surgical community [24, 25]. The constant increase in the number of patients requiring treatment has represented a massive challenge for many involved countries' healthcare systems and could be their breaking point. In an emergency situation, resources must be concentrated and used rationally to handle the pandemic and continue handling the pre-existing diseases. In this context, most surgical departments were forced to re-schedule their activity, giving priority to urgent/emergent surgical cases and non-deferrable oncological cases. There are many ways the outbreak of the Covid-19 pandemic could have influenced daily clinical practice for patients with biliary AP, leading to a failure to adhere to the recommendations coming from the guidelines, especially those regarding the early and definitive treatment with cholecystectomy or ERCP and sphincterotomy. First of all, the recommendation to postpone all non-urgent endoscopic procedures during the peak of the pandemic. Second, the recommendation to conservatively treat inflammatory conditions such as acute cholecystitis and acute appendicitis wherever possible.

#### The rationale for the study

Despite existing evidence-based practice guidelines for the management of biliary AP, in Europe, clinical compliance with recommendations is lacking. Studies in this field have identified significant discrepancies between evidence-based recommendations and daily clinical practice.

It is believed by many that clinical guidelines would help to decrease inappropriate variation in practice, that they provide a rational basis for referral, and that they would help to reduce uncertainty in the management of some conditions. Clinical guidelines also provide a basis for continuing medical education and can improve control of healthcare costs. However, the value of national and/or international guidelines is very much dependent on a strategy for their implementation. Although different guidelines for the management of biliary AP have been published, they have not been adequately investigated, and compliance has generally been unsatisfactory. Deficiencies and lack of standardization of the management of AP worldwide have been reported.

The most commonly reported gaps between clinical practice and AP guidelines include the indications for CT scan, need and timing of artificial nutritional support, indications for antibiotics, and surgical/endoscopic management of biliary AP.

The MANCTRA-1 can identify a number of areas for quality improvement that will require new implementation strategies. We aim to summarize the main areas of sub-optimal care due to the lack of compliance with current guidelines to provide the basis for introducing a number of bundles in AP patients' management to be implemented during the next years.

#### Aim of the study

Since the clinical compliance with recommendations about AP is poor and the impact of implementing guideline recommendations in biliary AP has not been well studied globally, we launched the MANCTRA-1 study intending to demonstrate areas where there is currently a sub-optimal implementation of current guidelines on biliary AP.

Moreover, we argue that during the Covid-19 pandemic, the tendency to disregard the guidelines recommendations has been more marked than usual, and we will try to find out if AP patients' care during the Covid-19 pandemic resulted in a higher rate of adverse outcomes compared to non-pandemic times due to the lack in the compliance of the guidelines.

#### Primary objective

! To evaluate which items of the current AP guidelines, if disregarded, correlate with

# negative clinical outcomes according to the different clinical presentations of the disease

#### Secondary objectives

- ! To assess the compliance of surgeons worldwide to the most up-to-date international guidelines on biliary AP
- ! To evaluate the medical and surgical practice in the management of biliary AP during the nonpandemic (2019) and pandemic Covid-19 periods (2020)
- ! To investigate outcomes of patients with biliary AP treatment during the two study periods

#### **Primary outcomes**

- ! 30-day mortality: assessed by the number of AP patients with biliary etiology deceased during the non-pandemic period (2019) and the Covid-19 pandemic period (2020)
- ! 30-day morbidity: assessed by the number of AP patients with biliary etiology who experienced any type of AP-related complication within 30-days from the hospital admission during the non-pandemic period (2019) and the Covid-19 pandemic period (2020)

#### Secondary outcomes

- ! Early definitive treatment rate in 2019 vs. 2020: defined as treatment in accordance with the current guidelines (cholecystectomy or ERCP with endoscopic sphincterotomy during the same hospital admission or within 2 weeks of discharge)
- ! 30-day hospital readmission rate in 2019 vs. 2020: defined as hospital readmission within 30days from discharge for recurrent biliary AP while awaiting interval cholecystectomy, or due to post-cholecystectomy complications
- ! Predictive factors of morbidity and mortality in patients with biliary AP

The compliance of surgeons to the most up-to-date international guidelines on biliary AP will be assessed through the analysis of the following attitudes:

! Use of scoring systems for the diagnosis and severity grading of biliary AP

- ! Use of lipase dosage (for the diagnosis) and CRP (for the severity grading) during the diagnostic workup
- ! Use of Ultrasound scan, CT scan, MRCP, and endoscopic Ultrasound scan (EUS) in the correct way and timing
- ! Use of early ERCP and sphincterotomy in case of cholangitis and/or choledocholithiasis
- ! Use of percutaneous and/or endoscopic drainage in case of infected pseudocyst or necrosis
- ! Timing of surgical necrosectomy
- ! Timing of re-laparotomy in case of open abdomen strategies
- ! Use of prophylactic antibiotics/antifungals
- ! Use of somatostatin analogs
- ! Use of early enteral feeding
- ! Use of early definitive treatment strategies, including cholecystectomy and/or ERCP and sphincterotomy

